Assess the enjoyment/motivation in performing the different training protocols, as well as adherence through analysis of dropout rates and the number of completed sessions.

Hypothesis:

We hypothesize that both groups will report improvements in physiological parameters, physical fitness, mental well-being, and overall quality of life compared to the WLCG. Additionally, the IMCT group will show superior improvements in physiological parameters compared to the MCT group.

CHARACTERISTICS OF PARTICIPANTS

The study aims to recruit at least 30 individuals with a history of cardiovascular problems, currently stable, aged between 45–80 years.

Inclusion Criteria

- Women/Men
- 45–80 years old
- Absence of severe medical conditions (unstable coronary artery disease, decompensated heart failure, severe pulmonary hypertension) or acute conditions that would prevent safe participation in physical activity according to the guidelines of the American College of Sports Medicine (ACSM), American Heart Association (AHA), and the European Society of Cardiology (ESC) (Billinger et al., 2014; Gary Liguori & ACSM, 2021; Pelliccia et al., 2021; Williams et al., 2007)
- History of cardiovascular dysfunctions currently stabilized
- Sedentary lifestyle (individuals not having followed WHO guidelines for aerobic and resistance exercise in the last 3 months)

Exclusion Criteria

- Smokers
- Expected absence for more than one week during the intervention period
- Absence of a medical certificate of suitability for non-competitive sports
- Severe musculoskeletal or joint disorders with significant mobility limitations

- Presence of joint pain, dizziness, chest pain, or angina during physical activity
- High blood pressure: PBP \geq 160/100 (untreated))

SAMPLE SIZE

A priori power analysis (Kang, 2021) with a Type I error of 0.05 and Type II error rate of 0.05 (95% statistical power) calculated that 10 participants per group would be sufficient to observe moderate interaction effects between “Time x Group.”

RECRUITMENT METHOD

Participants will be recruited through the "Amici di Cuore" association located at [name], and will be randomly assigned to one of three groups:

- MCT
- IMCT
- WLCG

data collection

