Before the intervention, all participants, with prior approval from their primary care physician, will sign an informed consent form. All participants will undergo physiological evaluations and functional tests before (T0) and at the end of the intervention (T1). Data will be collected anonymously, assigning each participant a random identification number.

Measurements:

Anthropometric Parameters:

- Height
- Weight
- BMI

Hemodynamic Parameters:

- Resting Heart rate (RHR)
- Peripheral Systolic Blood Pressure (P-SBP)
- Peripheral Dyastolic Blood Pressure (P-DBP)

Physical Parameters:

- Timed Up and GO (TUG)
- 30 Seconds Chair Stand Test (30”CST)
- 2 Minutes Step Test (TMST)
- Handgrip Strength Test (HGS)

Psychological Parameters:

- SF-36
- BREQ-3

Experimental Design

After initial evaluations, participants will be randomly assigned to one of the three groups. All protocols will last 24 weeks and take place at the Angiulli Artistic Gymnastics Society (Bari).

Sessions will be conducted in small groups. These groups will be closely supervised by exercise professionals, specialists in adapted physical activity (AFA), to ensure participant safety, maintain proper intensity, and correct execution technique. To monitor and regulate training intensity (internal load) during sessions, the Borg Perceived Exertion Scale (RPE) (6-20) will be used at the end of each exercise set to regulate the load to Borg = 13-15 points (Gary Liguori & ACSM, 2021). Participants will be familiarized with the scale beforehand.

Participants in the WLCG will not perform any structured physical activity during the entire intervention period, maintaining their usual lifestyle and placed on a waiting list to receive adapted physical activity after the 24-week intervention period.

Multi-component Training:

Each training session will include an initial muscle activation phase lasting 10 minutes (low-intensity walking, Borg = 10-11) to increase heart rate, improve muscle blood flow, and prepare the main joints for the subsequent work phase. This will be followed by a main 40-minute exercise period (aerobic exercise, mobility exercises, and resistance training) and a 10-minute cool-down period (breathing exercises and stretching).

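### Must the plan record cardiovascular drugs at T0 and T1 for the blood pressure and heart rate comparisons to be sound?

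*Combined protocol and SAP*

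**What the plan says.** All citations are to the combined protocol and SAP.

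- **Outcomes and timing.** Under data collection: "All participants will undergo physiological evaluations and functional tests before (T0) and at the end of the intervention (T1". The Hemodynamic Parameters are "Resting Heart rate (RHR", "Peripheral Systolic Blood Pressure (P-SBP" and the diastolic counterpart. The whole Measurements list has 3 anthropometric, 3 haemodynamic, 4 physical and 2 questionnaire items, 12 in all. None concerns drugs.
- **Who may enter.** The Inclusion Criteria ask for "History of cardiovascular dysfunctions currently stabilized". The Exclusion Criteria bar high blood pressure at "160/100 (untreated". No criterion bars drug treatment or requires it to stay constant.
- **Medical input.** Participants join "with prior approval from their primary care physician". The Exclusion Criteria require a medical certificate, and Risk Management Strategies requires a signed exercise clearance. All three concern fitness to take part, before training starts.
- **Arms.** Under Experimental Design: "Participants in the WLCG will not perform any structured physical activity during the entire intervention period". The Hypothesis section predicts that "the IMCT group will show superior improvements in physiological parameters compared to the MCT group".
- **Drugs.** The only mention is a general remark in Expected Results and Relevance that exercise may be used alongside drug therapy. It is not a data item.

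**The concern.** Drugs acting on blood pressure or heart rate move exactly the three haemodynamic outcomes, and in a population with a cardiovascular history many participants may take them. Participants know whether they train or wait, and nothing in the plan blinds their own doctors. If doctors raised treatment more often on the waiting list, or lowered it more often in the trained arms, the contrast with the waiting list would shrink; the reverse pattern would enlarge it. A small or null haemodynamic result would then be hard to interpret.

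The plan does not define physiological parameters, but these three measures plausibly carry much of that part of the main aim and of the predicted advantage of IMCT over MCT. For that second comparison the route is weaker: it needs a larger fall in IMCT to lead to more drug reduction there. Entry conditions such as stabilised disease and medical clearance may make drug changes less common, but they say nothing about the 24 weeks that follow.

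**Working it through.** The plan gives no figure for drug changes, drug effects or blood pressure variability. Its one computed figure, 10 per group, plays no part in the argument except as the arm size. The check has four steps.

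**1. What absence from the list shows.** The Measurements list is not a full data form. The secondary outcome needs dropout and completed sessions; eligibility needs age and smoking status. None of these is on the list, yet all must be collected. Likewise, applying the exclusion for untreated high blood pressure requires treated or untreated status at screening for anyone at that level. The accurate statement is therefore that the protocol does not say drugs are recorded. What is clearly unprovided for is drug name, dose, and any change after T0.

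**2. Size of the possible shift.** Assumptions: the net proportion with a drug change differs between two arms by 0.10, 0.20 or 0.30 (1, 2 or 3 of 10), and each change moves systolic pressure by 5-10 mmHg.

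Expected shift = difference in proportion × effect per change

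| Net difference | 5 mmHg per change | 10 mmHg per change |
|---|---|---|
| 0.10 | 0.5 | 1.0 |
| 0.20 | 1.0 | 2.0 |
| 0.30 | 1.5 | 3.0 |

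Against an assumed true training difference of 5-10 mmHg, this runs from 0.5/10 = 5% to 3.0/5 = 60%. The 60% needs the largest imbalance, the largest drug effect and the smallest training effect together. If changes do not differ by arm, the expected shift is zero.

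**3. Comparison with sampling error.** Assumption: SD of the T0-T1 change in systolic pressure of 8, 10 or 12 mmHg. With 10 per arm and 18 degrees of freedom (t = 2.101):

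Half-width = 2.101 × SD × √(2/10)

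- SD 8: 2.101 × 8 × 0.4472 = 7.5 mmHg
- SD 10: 2.101 × 10 × 0.4472 = 9.4 mmHg
- SD 12: 2.101 × 12 × 0.4472 = 11.3 mmHg

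The shift is thus between 0.5/11.3 = 4% and 3.0/7.5 = 40% of the half-width. Drug changes unrelated to arm are already inside the SD and need no separate treatment.

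**4. What a drug record could show.** Two-sided Fisher exact test with 10 per arm; the two tails are equal:

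- 2/10 v 0/10: 2 × C(10,2)/C(20,2) = 2 × 45/190 = 0.47
- 3/10 v 0/10: 2 × C(10,3)/C(20,3) = 2 × 120/1140 = 0.21

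Even the largest imbalance considered could not be told from chance. A further analysis that adjusted for, or restricted on, drug change would condition on an event after randomisation and be imprecise at this size, so it could only be exploratory. The Time x Group analysis would stay as it is.

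**The case for a change.** The strongest case for a change runs as follows. Imprecision is visible in the confidence interval, whereas a systematic shift is invisible unless drugs are recorded. The trained arms meet staff trained to recognise cardiovascular discomfort and the waiting list does not, so closer observation could itself alter prescribing. Data are held under random identification numbers, so drug histories may be hard to recover later. The cost is one form item at two existing visits and one table. And if no changes occurred, the table would strengthen the result.

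Much of this stands. The information would help a reader, it is cheap, and it is easier to collect at the visits than afterwards. What does not stand is the step from useful to necessary. The arm-related route is conjecture: the plan describes no blood pressure reading between T0 and T1 and no passing of trial readings to treating doctors, and session monitoring rests on the Borg scale and supervision. The route most readily argued, more treatment on the waiting list or less in the trained arms, dilutes the contrast, so it would not undermine a positive finding. And the shift is not a bias in the effect of assignment; it is part of that effect.

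**Conclusion.** No change to the plan is needed. The protocol does not say that cardiovascular drugs or their changes are recorded, and treated people may enter; the second point is inferred from the wording of the exclusion. But the plan followed as written gives a sound estimate of the effect of assignment on all three haemodynamic measures, and the other 9 of the 12 listed measures are not in question. Adding the record would alter no estimate, test or stated figure.

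The possible shift of 0.5-3.0 mmHg lies inside a half-width of roughly 7.5-11.3 mmHg. Both ranges rest wholly on assumed imbalance, drug effect and SD of change. This is a missing detail that a study team fills sensibly: noting the drugs that act on blood pressure or heart rate at each visit, and describing changes by arm beside the results, is ordinary good reporting. A report without it should present the haemodynamic differences as effects of assignment, whatever drug changes occurred.

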The cardiorespiratory training will consist of progressive aerobic exercises: controlled and rhythmic jumping jacks, step-ups on a stable platform (such as a low step or a stable surface), alternating knee lifts, rapid lateral steps, or lateral leg raises. Finally, 3 minutes of low-intensity walking will facilitate recovery for the next training phase.

The mobility training will consist of specific exercises (thoracic extensions, cat-cow, overhead stretching with a stick, and active internal hip rotations) targeting the main joints. These will be performed to the maximum (1 to 3 sets) but avoiding pain. The duration will gradually increase from 30 to 60 seconds per repetition, repeating from one to three times. Rest intervals of 30 to 60 seconds will be provided between sets and exercises.

The resistance training will consist of exercises targeting different muscle groups (8 exercises): quadriceps (leg extension with ankle weights/half squat with a chair), biceps (unilateral dumbbell curl), shoulders (dumbbell shoulder press), triceps (dumbbell French press), chest (dumbbell chest press/dumbbell flyes), and back (dumbbell rows). The resistance training program will follow the principle of gradual progressive load. Initially, participants will perform one set of 10-15 repetitions, which will increase to three sets of 10-15 repetitions during the intervention. Load adjustments will be made to ensure that the perceived effort (RPE) remains between 13 and 15 on the Borg Scale (6-20). During the protocol, participants will be given rest intervals of 60 to 120 seconds between sets and exercises. To prevent early muscle fatigue, exercises will be performed using an alternating training method based on muscle group division (upper body exercises will be performed in the first session and lower body exercises in the second).

The cool-down period will consist of breathing exercises and stretching. Stretching will be performed by seeking the maximum stretch on all the main muscle groups (1 to 3 sets per muscle group) while avoiding joint pain. The duration will gradually increase from 10 to 30 seconds per stretch, repeating from one to three times for a total of 60 seconds per exercise.

Isometric Multi-component Training:

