Each training session will include an initial phase of muscle activation lasting 10 minutes (low-intensity walking, Borg = 10-11) to increase heart rate, improve blood flow to muscles, and prepare the main joints for the subsequent work phase. This will be followed by a main 40-minute exercise period (aerobic exercise, mobility exercises, and isometric training) and a 10-minute cool-down period (breathing exercises and stretching). The cardiorespiratory training will consist of progressive aerobic exercises: controlled and rhythmic jumping jacks, step-ups on a stable platform (such as a low step or a stable surface), alternating knee lifts, quick lateral steps, or lateral leg raises. Finally, 3 minutes of low-intensity walking will facilitate recovery for the subsequent phase of training.

The mobility training will consist of specific exercises (thoracic extensions, cat-to-cow movements, overhead stretching with a stick, and active internal hip rotation) targeting the main joints, performed to the maximum (from 1 to 3 sets), while avoiding pain. The duration will gradually increase from 30 to 60 seconds per repetition, repeating from one to three times. Recovery intervals of 30 to 60 seconds will be allowed between sets and exercises.

The isometric training will focus on exercises targeting different muscle groups (8 exercises): quadriceps (isometric leg extension/wall squat), biceps brachii (isometric dumbbell curl), shoulders (isometric lateral raises with dumbbells), triceps brachii (isometric French press with dumbbells), pectoralis major (isometric dumbbell chest press/dumbbell flyes), latissimus dorsi (isometric dumbbell rows). The isometric training program will follow the principle of gradual progressive loading. Initially, participants will perform one set of 30 seconds, which will increase to three sets of 30 seconds over the course of the intervention. Load adjustments will be made to ensure that the perceived effort (RPE) stays between 13 and 15 on the Borg Scale (6-20). During the protocol, participants will be given recovery intervals of 60 to 120 seconds between sets and exercises. To prevent early muscle fatigue, exercises will be performed using an alternating training method based on splitting muscle groups (upper body exercises will be performed in the first session and lower body exercises in the second).

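### Do the stated sets, rests and mobility work overrun the 40-minute main period and so undermine the count of completed sessions?

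*Combined protocol and SAP*

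**What the plan says.** The Multi-component Training (MCT) section sets a "main 40-minute exercise period (aerobic exercise, mobility exercises, and resistance training"), and the Isometric Multi-component Training (IMCT) section sets a "main 40-minute exercise period (aerobic exercise, mobility exercises, and isometric training"). In both arms the aerobic part closes with a 3-minute walk. The length of the aerobic exercises themselves is not given.

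Strength work progresses in both arms. In MCT it starts at "one set of 10-15 repetitions, which will increase to three sets of 10-15 repetitions during the intervention"; in IMCT, "participants will perform one set of 30 seconds, which will increase to three sets of 30 seconds over the course of the intervention". The rests match: "participants will be given rest intervals of 60 to 120 seconds between sets and exercises" in MCT and "participants will be given recovery intervals of 60 to 120 seconds between sets and exercises" in IMCT. Each arm lists 8 strength exercises, with upper and lower body in alternate sessions.

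Mobility has four exercises in one to three sets. "The duration will gradually increase from 30 to 60 seconds per repetition, repeating from one to three times", and "Recovery intervals of 30 to 60 seconds will be allowed between sets and exercises".

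Under Secondary outcome, adherence is to be assessed from dropout rates and the number of sessions completed. Completion is not defined.

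**The concern.** A reader who adds up a late upper-body session with typical values gets more than 40 minutes before any aerobic exercise. If the listed content cannot fit, something must be shortened, and the protocol does not say what. A session that ends on time with content left over could be counted as completed or not, and that count feeds a named secondary outcome. If the two arms shortened different parts, the contrast between IMCT and MCT would also be harder to attribute to the isometric component. The cool-down looked inconsistent too: one to three stretches of 10 seconds give 10 to 30 seconds, against a stated total of 60 seconds per exercise.

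**Working it through.** **Inputs.** All come from the MCT and IMCT sections. Counting each item on either side of a slash as an exercise gives 6 upper-body and 2 lower-body exercises, which matches the stated 8. Treating chest press and flyes as alternatives gives 5 upper-body exercises. The IMCT hold is 30 s, strength rests are 60–120 s, mobility is 4 exercises of 1–3 × 30–60 s with 30–60 s rests, and the walk is 3 min. No time is counted for changes between blocks.

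**Formula.** Block time = (number of sets × work time) + (number of sets − 1) × rest.

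**IMCT strength block, three sets, rests of 60 / 90 / 120 s**
- Six exercises: 18 × 0.5 = 9 min of holds, plus 17 rests = 17 / 25.5 / 34 min. Block: 26 / 34.5 / 43 min.
- Five exercises: 15 × 0.5 = 7.5 min, plus 14 rests = 14 / 21 / 28 min. Block: 21.5 / 28.5 / 35.5 min.

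**Mobility block**
- 1 × 30 s, 30 s rests: 2 + 1.5 = 3.5 min
- 1 × 60 s, 30 s rests: 4 + 1.5 = 5.5 min
- 3 × 30 s, 30 s rests: 6 + 5.5 = 11.5 min
- 2 × 45 s, 45 s rests (midpoints): 6 + 5.25 = 11.25 min
- 3 × 60 s, 60 s rests: 12 + 11 = 23 min

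**IMCT upper-body totals at three sets, walk included, aerobic exercises excluded (minutes, against 40)**

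| Scenario | Six exercises | Five exercises |
|---|---|---|
| All ranges at the low end | 26 + 3.5 + 3 = 32.5 | 21.5 + 3.5 + 3 = 28.0 |
| 60 s rests, mobility 1 × 60 s | 26 + 5.5 + 3 = 34.5 | 21.5 + 5.5 + 3 = 30.0 |
| 60 s rests, mobility 3 × 30 s | 26 + 11.5 + 3 = 40.5 | 21.5 + 11.5 + 3 = 36.0 |
| All ranges at midpoint | 34.5 + 11.25 + 3 = 48.75 | 28.5 + 11.25 + 3 = 42.75 |
| All ranges at the high end | 43 + 23 + 3 = 69 | 35.5 + 23 + 3 = 61.5 |

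The second row matters most. It has the strength progression at three sets and the mobility hold at 60 s, and it leaves 5.5 min (six exercises) or 10 min (five) for aerobic work. With six exercises and that mobility, the total reaches 40 min when the mean rest is (40 − 3 − 5.5 − 9)/17 min = 79 s, which lies inside the stated range.

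**Other IMCT sessions at midpoints**
- Two sets, six exercises: 6 + 16.5 + 11.25 + 3 = 36.75 min.
- Three sets, lower body (two exercises): 3 + 7.5 + 11.25 + 3 = 24.75 min.

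**MCT, three sets, six exercises**
- Low end before any repetition: 17 + 3.5 + 3 = 23.5 min. Repetition time is not stated. Assuming 2–4 s and 12.5 repetitions per set, 18 sets add 7.5–15 min, for 31–38.5 min.
- Midpoints before any repetition: 25.5 + 11.25 + 3 = 39.75 min (35.25 with five exercises).

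**Cool-down.** The text allows both one to three sets per muscle group and one to three repeats. Two sets × three repeats × 10 s = 60 s; 20 s × 3 and 30 s × 2 also give 60 s. The stated total can be reached at the start of the progression as well as later.

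**The case for a change.** The strongest case for a change is that midpoints are not a worst case. Mobility holds lengthen to 60 s, so 45 s understates late sessions. With six exercises, the count that matches the stated 8, three mobility repeats fit at no stated duration or rest: the shortest version takes 40.5 min with no aerobic exercise. At 3 × 60 s and the shortest rests, IMCT takes 26 + 17.5 + 3 = 46.5 min with six exercises and 21.5 + 17.5 + 3 = 42.0 min with five. The protocol does not say that late sessions keep to the low end or what gives way when time runs out.

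The arithmetic stands, and so does the observation that the upper values cannot all be used together. But no sentence requires them to be. Mobility may be done once, and 60 s rests are allowed. Setting every range to its midpoint is one scenario, not a plan the protocol states. The ranges are limits within which specialist supervisors work, adjusting load to the Borg rating.

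The lack of a definition of a completed session also stands. It would be there however long the sessions were, so the timing sums add nothing to it. An analyst would read it as attendance and apply it alike in both arms.

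On attribution, the aerobic and mobility parts are described in nearly the same words for both arms, and nothing shows that one arm would lose more shared time than the other.

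**Conclusion.** The 40-minute figure is tight but not contradicted. Late upper-body IMCT sessions run from 32.5 to 69 min with six exercises (28.0 to 61.5 with five) across the stated ranges, before the aerobic exercises, so part of the range fits and part does not. The pressure falls on upper-body sessions at the three-set stage; lower-body and two-set IMCT sessions fit even at midpoints. Neither the week in which three sets are reached nor the weekly frequency is given, so the number of sessions concerned cannot be estimated.

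What remains is missing detail: the aerobic minutes and a definition of a completed session. Supervisors can settle the first within the ranges given, and analysts the second by counting attendance identically in both arms. The comparisons of MCT, IMCT and waitlist do not depend on either, so a change would bring no gain in the results. The choice of values within the ranges belongs to the investigators.

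This rests on reading the set, rest and mobility figures as limits, on counting no time between blocks, and, for MCT, on an assumed 2–4 s per repetition.
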